8.6.3.2 Dose Adjustment of Study Product During Up-Dosing and Maintenance

Actions that may be taken with study product dosing for allergic reactions during up-dosing and maintenance include the following:

- Administer the next dose of study product at the study site under medical supervision.
- Split the daily dose of study product into 2 portions (may be unequal) given 8 to 12 hours apart.
- Delay the study product dose escalation an additional 1 to 2 weeks.

- Reduce the study product dose level by 1 or 2 dose levels.
- Temporarily withhold study product.
- Stop study product dosing and discontinue the subject early from the study ([Section 5.3](#)).

The severity of the symptoms will guide study product dose reductions for both acute and chronic or recurrent symptoms. The process algorithm for dose adjustments for dose-related symptoms occurring at a new dose or dose level given at the study site or for symptoms of a dose-related allergic reaction reported during daily dosing at home is shown in [Figure 3](#) and described in [Table 12](#).

When study product dose-related allergy symptoms occur at home, the parent/caregiver must report the symptoms to the study site to determine whether the next dose should be administered at home or at the study site. Administration of study product at the study site under medical supervision is strongly encouraged any time that acute allergy symptoms are reported, including mild symptoms occurring with a dose that is suspected to be not tolerated.

The dose escalation may be delayed or the dose level reduced if the tolerability of a dose level is uncertain, at investigator discretion ([Section 8.6.1.2](#)).

In general, a reduced dose of study product is to be given at the study site under medical supervision and continued for 2 weeks at home. The lowest dose level of study product is 1 mg.

[figure not shown]
Symptomatic treatment should be used to supplement dose reduction and not as a substitute for it. Symptomatic treatment of adverse events should be discontinued before attempting dose re-escalation at the study site. However, if treatment for chronic or recurrent adverse events cannot be withdrawn successfully, it may be administered concurrently with study product dose re-escalation.

A dose re-escalation attempt should be made within 4 weeks after a dose reduction, unless dose escalation is to be delayed further due to administration of epinephrine ([Table 13](#)).

Study product dosing will stop and the subject will discontinue early ([Section 5.3](#)) if any of the following conditions are met for dose adjustment:

- The dose level cannot be escalated after 3 consecutive failed attempts with at least 2 weeks between each escalation attempt.
- The reduced dose of study product cannot be tolerated after 3 attempts to reduce the dose level.

Figure 3: Management of Study Product Dosing for Allergy Symptoms During Up-Dosing and Maintenance

Assess dose tolerability per [Section 8.6.1.2](#).

[1] The actions for moderate symptoms assessed as tolerated are the same as for a dose or dose level associated with mild symptoms assessed as tolerated.

Table 12: Description of Actions to Be Taken With Study Product Dosing for Allergy Symptoms During Up-Dosing and Maintenance

Symptoms [1]	Actions
Mild	
For oral/pharyngeal pruritus occurring in isolation, continue the study product dose level at home for the 2-week dosing interval, unless other symptoms develop.
 
For other mild symptoms and if the study product dose is assessed as tolerated (Section 8.6.1.2), repeat the same dose level the next day, ideally at the study site although it may be given at home.
 
 • If no symptoms occur with the repeated dose, continue the dose level for the 2-week dosing interval. • If mild symptoms occur with the repeated dose and the dose is assessed as tolerated, continue the same dose level or reduce the dose to the previous tolerated dose level for the 2-week dosing interval. 
For other mild symptoms and if the study product dose is assessed as not tolerated (Section 8.6.1.2), give the previous tolerated dose level the next day at the study site.
 
 • If the reduced dose is tolerated, continue the dose level for the 2-week dosing interval. • If the reduced dose is assessed as not tolerated, give a second reduced dose (1 or 2 dose levels lower) the next day at the study site. 
 – If the second reduced dose is tolerated, continue this dose level for the 2-week dosing interval. – If the second reduced dose is assessed as not tolerated, discuss early discontinuation with the medical monitor. – If a third reduced dose is considered to be safe after discussion with the medical monitor, give it at the study site under medical supervision. If the dose is assessed as not tolerated, stop study product dosing and discontinue the subject early from the study (Section 5.3). 
For other mild symptoms and if the study product dose tolerability is uncertain, follow the general guidance in this table for chronic or recurrent mild symptoms.

Mild (chronic or recurrent)	
The recurrence of mild dose-related symptoms over several days of dosing at home may suggest that the study product dose level is not tolerated, even if each dose could be assessed as tolerated.
 
 • For symptoms occurring \geq 4 times in a week, give the next dose of study product at the study site to assess tolerability. • For symptoms occurring \geq 7 times during the 2-week dosing interval, the dose level will be considered not tolerated (Section 8.6.1.2). 
Other actions that may be taken for chronic or recurrent mild symptoms:
 
 • Continue daily dosing at home at the current dose level. • Continue the same daily dose for the rest of the 2-week dosing interval, split into 2 portions (may be unequal) and given 8 to 12 hours apart. • Repeat the same dose level at the study site to assess tolerability. • Delay the dose escalation by 1 to 2 weeks. • Give the previous tolerated dose level (1 or 2 dose levels lower based on severity of reaction) at the study site. • Stop study product dosing and discontinue the subject early from the study (Section 5.3). 
GI symptoms
 
For chronic or recurrent GI symptoms, especially upper GI symptoms, a low threshold for study product dose reduction and for considering early discontinuation is recommended due to the potential for eosinophilic esophagitis. For dose-limiting

Symptoms [1]	Actions
	
chronic or recurrent GI symptoms at doses \leq 20 mg/day, withhold study product for 4 weeks and resume at 1 mg/day with the first dose given at the study site. If 1 mg/day is tolerated, continue this dose level for at least 4 weeks before attempting re-escalation.
 
For dose-limiting chronic or recurrent GI symptoms at doses $>$ 20 mg/day, follow the general guidance in this table based on symptom severity.

Moderate	
Administer the previous tolerated dose of study product the next day at the study site.
 
 • If no symptoms occur with the reduced dose, continue that dose level for 2 weeks before attempting re-escalation. • If mild symptoms occur at the reduced dose, follow the guidelines for mild symptoms. • If moderate symptoms occur at the reduced dose, give a second reduced dose (1 or 2 dose levels lower) the next day at the study site. 
 – If the second reduced dose is tolerated, continue that dose level for at least 2 weeks before attempting re-escalation. – If mild symptoms occur with the second reduced dose that is assessed as not tolerated, follow the guidelines for mild symptoms. – If moderate symptoms recur at the second reduced dose, discuss early discontinuation with the medical monitor. 
 ▪ If a third reduced dose is considered to be safe after discussion with the medical monitor, give it at the study site under medical supervision. If the dose is assessed as not tolerated, stop study product dosing and discontinue the subject early from the study (Section 5.3). 
In the rare case that a dose with moderate symptoms is assessed as tolerated, follow the guidelines for mild symptoms and provide a brief explanation for the assessment on the case report form.

Severe	
Discuss early discontinuation with the medical monitor. If continuation of study product is considered to be safe, administer a reduced dose at 2 dose levels the next day at the study site under medical supervision. If the reduced dose is tolerated, continue that dose level for at least 2 weeks before attempting re-escalation. If the reduced dose is assessed as not tolerated, stop study product dosing and discontinue the subject early from the study (Section 5.3).

Life-threatening	
Stop study product dosing and discontinue the subject early from the study (Section 5.3).

Assess dose tolerability per [Section 8.6.1.2](#).

[1] Depending on the subject's stage of development, allergy symptoms may be difficult to interpret. Age-appropriate allergy symptoms should be considered when determining the appropriate actions to be taken with study product dosing.

GI, gastrointestinal.

Appropriate intervention for allergy symptoms associated with a new dose or dose level at the study site or dosing at home will depend on the type and severity of symptoms. The process algorithm for dose adjustments after administration of antihistamines and epinephrine for dose-related allergy symptoms at the study site or at home during up-dosing is described in [Table 13](#).

Table 13: Dose Adjustment of Study Product After Treatment With Antihistamines and Epinephrine for Dose-Related Allergy Symptoms During Up-Dosing

Medications	Action
Antihistamines	Continue study product up-dosing if symptoms only require antihistamines. If symptoms during up-dosing at the study site or at home require > 2 doses of antihistamine alone or in combination with other medications (except epinephrine), reduce the next dose of study product by 1 or 2 dose levels and give it at the study site under medical supervision. If no symptoms occur at the reduced dose, continue up-dosing for the 2-week dosing interval.
Epinephrine	If an administration of epinephrine is required during dose escalation at the study site, reduce the next dose of study product by 2 dose levels and give it at the study site under medical supervision. After 2 weeks at the reduced dose, dose re-escalation at 1 dose level may be attempted at the study site. If epinephrine is required a second time, reduce the next dose of study product by 2 dose levels and give it at the study site under medical supervision. After 6 to 8 weeks at the reduced dose, dose re-escalation at 1 dose level may be attempted at the study site. If epinephrine is required a third consecutive time for dose-related allergy symptoms during a dose escalation attempt at the study site or at home, stop study product dosing and discontinue the subject early from the study (Section 5.3). If epinephrine is given at home, the parent/caregiver is to call emergency medical services and the subject is to be taken to the nearest emergency department immediately. Reduce the next dose of study product by 1 or 2 dose levels and give it at the study site under medical supervision before resuming dosing at home.

8.6.4 Dose Adjustment of Study Product for Reasons Other Than Allergic Reactions to Study Product

The study product dose level may be continued or reduced, or the dose withheld per investigator judgment in the event of a flare of asthma or atopic disease (eg, atopic dermatitis) not related to study product, or intercurrent illness.

The amount of dose reduction may range from 1 dose level (ie, the previous dose level) to approximately 50% (rounded down to the nearest feasible whole dose) at the discretion of the investigator. The lowest dose level is 1 mg.

If the dose is reduced for reasons other than allergic reactions to study product, the reduced dose will be given for 2 weeks and the subject is to be fully recovered (ie, baseline status) for at least 3 days, depending on the severity of the illness per investigator assessment, before attempting dose re-escalation at the study site. Treatment for an intercurrent illness or disease should be discontinued before dose re-escalation. However, if the treatment cannot be withdrawn successfully, it may be administered concurrently with study product.

The process of dose re-escalation for reduced doses due to reasons other than allergic reactions will depend on the degree and duration of the dose reduction as described in [Table 14](#). A dose re-escalation attempt should be made within 4 weeks after a dose reduction.

The study product may also be withheld as part of the treatment for intercurrent adverse events at the discretion of the investigator; dose continuation after temporary withholding will follow the procedure for missed study product doses ([Section 8.6.5](#)).

Study product dosing will stop and the subject will discontinue early from the study ([Section 5.3](#)) if any of the following conditions for dose adjustment are met:

- The dose level cannot be escalated after 3 consecutive failed attempts with at least 2 weeks between each escalation attempt.
- The reduced dose of study product cannot be tolerated after 3 attempts to reduce the dose level.

Table 14: Study Product Dose Re-Escalation After Dose Reduction for Reasons Other Than Allergic Reactions

Dose Reductions	Action
1-4 consecutive days	Next dose at the previous dose level under medical supervision at the study site, and continue the 2-week dosing interval.
5-7 consecutive days	Next dose under medical supervision at the study site at the reduced dose level or the previous dose level. If re-escalation is tolerated, continue the dose level for at least 2 weeks before attempting re-escalation.
8-14 consecutive days	Next dose under medical supervision at the study site at the reduced dose level or 1 dose level above. If re-escalation is tolerated, continue the dose level for at least 2 weeks before attempting re-escalation.

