8.6.1.2 Assessment of the Tolerability of a Study Product Dose or Dose Level

The tolerability of a study product dose or dose level will be assessed based on the occurrence of acute allergy symptoms after dosing. When multiple symptoms are present, the severity of the most severe symptom will be used to determine whether symptoms are dose limiting and the dose or dose level is tolerated. Possible assessments of symptom severity, dose-limiting symptoms, and dose tolerability are shown in [Table 10](#).

Table 10: Allergy Symptom Severity and Study Product Dose Tolerability

Symptom Severity [1]	Dose-Limiting Symptom	Assessed Tolerability of Dose
None	No	Tolerated
Mild, oropharyngeal symptoms only	No	Tolerated
Mild, meeting tolerability criteria	No	Tolerated
Mild, not meeting tolerability criteria	Yes	Not tolerated
Moderate, with rare exceptions	Yes	Not tolerated
Severe	Yes	Not tolerated
Life-threatening	Yes	Not tolerated

[1] Depending on the subject's stage of development, allergy symptoms may be difficult to interpret. Age-appropriate allergy symptoms should be considered when assessing the tolerability of a dose.

No Symptoms: A study product dose associated with no allergy symptoms will be assessed as tolerated.

Mild symptoms: For a study product dose associated with mild allergy symptoms, investigator assessment is essential in determining if the symptoms are dose limiting. Based on experience with study product, mild symptoms are not dose limiting if they meet all of the tolerability criteria as follows:

- Are isolated to a single organ system
- Resolve with no medications or with ≤ 2 doses of oral H1 antihistamine
- Do not require administration of epinephrine
- Do not worsen in intensity or distribution over time
- Resolve or show definite signs of resolving in under 1 hour
- Do not include objective wheezing

The study product dose is to be considered not tolerated if mild symptoms do not meet the tolerability criteria as follows:

- Occur in 2 or more organ systems
- Require treatment with 3 doses of oral H1 antihistamine or 1 dose of epinephrine
- Progress in severity or distribution over time
- Continue longer than expected
- Include objective wheezing

If a study product dose associated with mild symptoms that do not meet the tolerability criteria is assessed as tolerated by the investigator, an explanation must be provided on the case report form.

Guidelines for recurrent mild symptoms:

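### For mild isolated mouth or throat itching, Tables 10 and 12 treat the dose as tolerated and continue it at home, even where the Section 8.6.1.2 text calls it not tolerated

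*Combined protocol and SAP*

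**What the plan says.** Four places in the protocol bear on mild itching confined to the mouth or throat.

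- **Section 8.6.3.2, Table 12, Mild row:** "For oral/pharyngeal pruritus occurring in isolation, continue the study product dose level at home for the 2-week dosing interval, unless other symptoms develop". The only exception is the appearance of other symptoms. The reduced-dose step in the same row opens "For other mild symptoms and if the study product dose is assessed as not tolerated", so it excludes isolated itching.
- **Section 8.6.1.2, Table 10:** the row "Mild, oropharyngeal symptoms only" is marked not dose-limiting and tolerated. It stands apart from the next row, "Mild, meeting tolerability criteria", so on its face it does not depend on the criteria.
- **Section 8.6.1.2, text on mild symptoms:** all the tolerability criteria must be met. A dose is to be considered not tolerated if the symptoms, among other things, "Require treatment with 3 doses of oral H1 antihistamine or 1 dose of epinephrine", progress, or go on longer than expected. No oropharyngeal exemption is stated. The investigator may still assess such a dose as tolerated, with an explanation on the case report form.
- **Section 8.6.3.2, Table 13, antihistamine row:** the rule starts once the antihistamine count goes above two, and its wording runs "doses of antihistamine alone or in combination with other medications (except epinephrine), reduce the next dose of study product by 1 or 2 dose levels". The reduced dose is then taken under supervision at the site.

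**The concern.** These rules govern home dosing of an allergen in children aged 1 to under 4 years, an age at which the protocol itself warns that allergy symptoms may be hard to interpret. Read literally, the Table 12 line keeps a child on the full dose at home after a reaction that the text of Section 8.6.1.2 calls not tolerated. Two sites could handle the same event differently, and each could cite the protocol. The matter is dosing safety and consistency between sites, not the analysis.

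**Working it through.** The protocol gives no figure to reproduce here, so the check traces the rules for one event.

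**Which criteria can isolated itching fail?** Being isolated, it meets the single-organ criterion and involves no wheezing. It can still need more than 2 antihistamine doses, need epinephrine, worsen, or not be resolving within 1 hour. The conflict is therefore wider than antihistamine use.

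| Source | More than 2 antihistamine doses | Worsens or persists, 2 or fewer doses |
|---|---|---|
| Table 12 | same level at home | same level at home, unless other symptoms develop |
| Table 10 | tolerated | tolerated |
| Section 8.6.1.2 text | not tolerated (override possible) | not tolerated (override possible) |
| Table 13, up-dosing | reduce 1 or 2 levels, at site | not triggered |
| Table 13, maintenance | does not apply | does not apply |

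Where every criterion is met, the sources agree.

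**Scope.** Table 12 is titled "Description of Actions to Be Taken With Study Product Dosing for Allergy Symptoms During Up-Dosing and Maintenance". Table 13 is titled "Dose Adjustment of Study Product After Treatment With Antihistamines and Epinephrine for Dose-Related Allergy Symptoms During Up-Dosing", which leaves out maintenance.

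**Up-dosing.** After more than 2 antihistamine doses, the Table 12 and Table 13 actions cannot both be followed, and no sentence ranks them. An investigator override changes the tolerability assessment but does not cancel the Table 13 reduction.

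**Maintenance.** A site that follows the text and assesses the dose as not tolerated turns to Table 12 and finds that the reduced-dose step is written for other mild symptoms. The footer of Table 12 refers back to Section 8.6.1.2, where Table 10 and the text differ. The recurrent-symptom row starts only at 4 events in a week. The same gap arises in up-dosing when the failed criterion is not a medication one.

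**Dose at stake.** Levels (Section 3.1): 1, 3, 6, 12, 20, 40, 80, 120, 160, 200, 240, 300 mg.
- Maintenance, if the previous tolerated level is one level down: 300/240 = 1.25.
- Up-dosing, current level over one level down: from 240/200 = 1.2 to 3/1 = 3.0.
- Up-dosing, current level over two levels down: from 300/200 = 1.5 to 6/1 = 6.0.

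**Time at stake if the dose is reduced.** This assumes 2 weeks per level and no further reaction.
- Up-dosing slack (Section 5.2.3.2): 40 − 24 = 16 weeks.
- A one-level cut costs 2 weeks (event on the first day at a level) to 2 + 2 = 4 weeks (event at the end of the interval). A two-level cut costs 4 to 6 weeks.
- Event at the end of maintenance: 2 to 4 weeks at the reduced dose (re-escalation is to be attempted within 4 weeks) plus the 2 weeks at 300 mg required before the exit challenge (Section 5.2.3.3) gives a delay of 4 to 6 weeks.
- For a child already at the 24-week maintenance maximum: 24 + 4 = 28 to 24 + 6 = 30 weeks.

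**The case against.** The strongest reply is that the protocol already handles this. Table 12 is organised by severity and Table 13 by treatment given, so once more than 2 antihistamine doses are used in up-dosing the treatment-specific rule takes over. In both periods, home symptoms must be reported to the site, site dosing after acute symptoms is strongly encouraged, and the investigator may reduce the dose when tolerability is uncertain. Table 10 is introduced as a set of possible assessments, so its oropharyngeal row need not override the explicit text, or it may be a deliberate exemption. Figure 3, which shows the same algorithm, is not in the text reviewed and may separate the cases.

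Much of this stands. Table 13 would probably govern in up-dosing. A reader might infer that children in up-dosing are in practice kept at full dose at home after 3 antihistamine doses, but the documents do not support that. They also do not support replacing the investigator's judgement with a mandatory not-tolerated assessment, because Section 8.6.1.2 expressly permits an explained override. Table 11 does put a limit of 2 antihistamine doses beside its itching line, but it governs supervised first exposure and is only a partial precedent.

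What does not stand is that these safeguards remove the conflict. They are discretionary, or they concern where the dose is given rather than its level. If the Table 10 row is a deliberate exemption, the text should say so. Figure 3 cannot cancel the wording of Table 12.

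**Conclusion.** The conflict holds as a low-impact dosing-safety correction. Tables 10 and 12 disagree with the Section 8.6.1.2 text whenever mild isolated itching fails a tolerability criterion. In up-dosing, Table 12 also disagrees with Table 13 after more than 2 antihistamine doses. In maintenance, no action is named for isolated itching assessed as not tolerated.

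The practical effect is probably small. The maintenance difference is 1.25-fold, in a child who had to tolerate 300 mg/day for 2 weeks to enter that period. The dose ratios are arithmetic on the dosing schedule and are not evidence of harm. The documents give no frequency for such events. A reader might go on to infer a bias in the exit-challenge response rate or a loss of power; nothing in the documents supports either, and neither is claimed. The conclusion rests on the wording of the tables and text, with Figure 3 unseen.

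**What to change.** 1. **Table 12, itching line.** Limit it to isolated itching where the dose has been assessed as tolerated under Section 8.6.1.2. Add that in up-dosing Table 13 governs if more than 2 antihistamine doses or any epinephrine is needed. Add that a dose assessed as not tolerated follows the not-tolerated steps in the same row. The pointer is needed because those steps now cover only other mild symptoms.
2. **Table 10, oropharyngeal row.** Add a limit of no more than 2 antihistamine doses and no epinephrine. Then either apply the remaining criteria to this row or state in the Section 8.6.1.2 text that isolated oropharyngeal symptoms are exempt from them.
3. **Override.** Keep it, with its case report form explanation.
4. **Figure 3.** Align it if it differs.

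**Cost.** The change is one table line, one table row, possibly one sentence of text, and a note to sites. In up-dosing, events needing more than 2 antihistamine doses add no visit beyond what Table 13 already requires. If the remaining criteria are applied, itching that fails one of them would also bring a supervised reduced dose and use some of the 16 weeks of slack.

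In maintenance, each not-tolerated event adds a supervised reduced-dose visit and a re-escalation visit, which may coincide with a 4-weekly visit. An event at the very end could delay the exit challenge by about 4 to 6 weeks. For a child already at 24 weeks of maintenance this exceeds the stated maximum. Appendix 3, Section 5 links the maximum durations to responder status and makes an exception only for time affected by emergency restrictions. The amendment should therefore allow for this delay explicitly.

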3 INVESTIGATIONAL PLAN

3.1 Overall Study Design and Plan: Description

This is a phase 3, international, randomized, double-blind, placebo-controlled study of the efficacy and safety of AR101 in peanut-allergic children aged 1 to < 4 years. The study will be conducted at approximately 25 study sites in North America and Europe.

Eligible subjects who develop age-appropriate dose-limiting allergy symptoms after consuming single doses of peanut protein > 3 mg to \leq 300 mg in a screening DBPCFC will be randomly assigned 2:1 to blinded treatment with AR101 or placebo. Randomization will be stratified by geographic region (North America, Europe).

Subjects will begin initial dose escalation under medical supervision at the study site on day 1 with a stepwise dose escalation of study product (up to 4 single doses of 0.5, 1, 1.5, and 3 mg) administered at 20- to 30-minute intervals as tolerated. Subjects who tolerate the 3 mg dose on day 1 will return on day 2 for a single 1 mg dose. Subjects who tolerate the 1 mg dose with no more than mild allergy symptoms that are not dose-limiting will begin the up-dosing period. Subjects who do not tolerate any dose on day 1 or day 2 will discontinue early from the study.

The up-dosing period will be approximately 6 months (maximum 40 weeks), with dose escalation approximately every 2 weeks. Daily doses of study product during up-dosing will be 1, 3, 6, 12, 20, 40, 80, 120, 160, 200, 240, and 300 mg/day. The first dose of study product at each new dose level will be administered under medical supervision at the study site; the remaining doses at each dose level will be administered daily at home as tolerated. Dose adjustments may be allowed. Subjects who tolerate the 300 mg/day dose for 2 weeks within 40 weeks will begin the maintenance period. Subjects unable to tolerate the 300 mg/day dose for 2 weeks within 40 weeks of up-dosing will discontinue early from the study.

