8.6.2 Treatment of Allergic Reactions

Treatment of allergic reactions is guided by the type of symptoms and severity as determined by the investigator, and supplements dose adjustment. Rescue medications for acute allergic reactions include antihistamines, epinephrine, IV fluids, a beta-agonist (eg, albuterol by inhaler or nebulizer), oxygen, and glucocorticosteroids as indicated ([Section 7.3](#)).

Mild acute allergic reactions are mostly transient and self-limiting and require no therapeutic intervention, whereas other reactions may require treatment (generally antihistamines).

Treatment for chronic or recurrent allergic reactions should be used minimally and discontinued as soon as clinically appropriate. Treatment for chronic or recurrent allergic reactions should not be started in advance of symptoms; however, exceptions may be allowed on a case-by-case basis following approval from the medical monitor.

Moderate acute allergic reactions will generally require therapeutic intervention; some rare events may be so transient that no specific treatment is required. For moderate reactions requiring treatment, antihistamines and/or epinephrine is to be administered as indicated.

Severe acute allergic reactions will generally require treatment with epinephrine.

Life-threatening acute allergic reactions will require treatment at an emergency facility as appropriate and consistent with good medical practice.

If the severity of the reaction is uncertain, epinephrine administration is likely appropriate.

A medical monitor will be available to answer questions or to assist in decisions related to the study protocol.

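### During up-dosing, Tables 12 and 13 give different next doses for the same treated reaction in two foreseen cases, and the protocol does not say which table prevails

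*Combined protocol and SAP*

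**What the plan says.** Section 8.6.3.2 presents both tables as the algorithm for adjusting study product after dose-related symptoms at the site or at home. Table 13 is limited to up-dosing, so a treated reaction in that period falls under both.

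**Table 12, by severity**
- Moderate: "Administer the previous tolerated dose of study product the next day at the study site".
- Mild but not tolerated: also the previous tolerated level, next day, at the site.
- Severe: discuss discontinuation with the medical monitor and, if dosing goes on, "administer a reduced dose at 2 dose levels the next day at the study site under medical supervision".

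**Table 13, by medication**
- Antihistamines alone: "Continue study product up-dosing if symptoms only require antihistamines".
- More than 2 antihistamine doses, without epinephrine: "reduce the next dose of study product by 1 or 2 dose levels and give it at the study site under medical supervision".
- Epinephrine at the site: "If an administration of epinephrine is required during dose escalation at the study site, reduce the next dose of study product by 2 dose levels".
- Second epinephrine use: 2 levels down and 6 to 8 weeks at the reduced dose, with no location given for the reaction.
- Epinephrine at home: the same 1-or-2-level wording as for more than 2 antihistamine doses, with no period at the reduced dose.

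Section 8.6.2 allows either drug for a moderate reaction: "For moderate reactions requiring treatment, antihistamines and/or epinephrine is to be administered as indicated". Section 8.6.1.2 classes mild symptoms as not tolerated if, for example, they involve 2 organ systems or need a dose of epinephrine. The protocol therefore foresees all of these combinations.

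**The concern.** One table is indexed by severity and the other by treatment. A reaction has both attributes, so a site must look it up twice, and in some cells the answers differ. Two sites that each follow the protocol could then give different doses, on the day after the same reaction, to children aged 1 to < 4 years.

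There is also a consequence for the analysis. Each reduction uses part of the time allowed for up-dosing. A child who does not tolerate 300 mg/day for 2 weeks within 40 weeks discontinues (Section 5.2.3.2) and counts as a nonresponder in the primary analysis (Section 10.5.1). The choice of table can therefore bear on the endpoint as well as on the dose.

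**Working it through.** **Inputs.** The ladder comes from Section 3.1: "Daily doses of study product during up-dosing will be 1, 3, 6, 12, 20, 40, 80, 120, 160, 200, 240, and 300 mg/day". The floor comes from Section 8.6.3.2: "The lowest dose level of study product is 1 mg". The previous tolerated dose is read as 1 level down, which is an assumption. The steps in Table 3, 100 × (dose / previous dose − 1), reproduce as 200, 100, 100, 67, 100, 100, 50, 33, 25, 20 and 25%, all as printed.

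**Side by side, with severity and treatment held fixed**

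| Reaction and treatment | Table 12 | Table 13 | Conflict |
|---|---|---|---|
| Moderate or mild-not-tolerated, 1–2 antihistamine doses only | 1 down | continue | yes (case 1) |
| Moderate or mild-not-tolerated, epinephrine at site | 1 down | 2 down | yes (case 2) |
| Severe, epinephrine at site | 2 down after monitor discussion | 2 down | none on size |
| Severe, epinephrine at home | 2 down after monitor discussion | 1 or 2 down | 2 down satisfies both |

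**Size of the two conflicts.** The case 1 ratio is current dose / 1 down. The case 2 ratio is 1 down / 2 down.

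| Level (mg) | 1 down | 2 down | Case 1 | Case 2 |
|---|---|---|---|---|
| 1 | 1 | 1 | 1.00 | 1.00 |
| 3 | 1 | 1 | 3.00 | 1.00 |
| 6 | 3 | 1 | 2.00 | 3.00 |
| 12 | 6 | 3 | 2.00 | 2.00 |
| 20 | 12 | 6 | 1.67 | 2.00 |
| 40 | 20 | 12 | 2.00 | 1.67 |
| 80 | 40 | 20 | 2.00 | 2.00 |
| 120 | 80 | 40 | 1.50 | 2.00 |
| 160 | 120 | 80 | 1.33 | 1.50 |
| 200 | 160 | 120 | 1.25 | 1.33 |
| 240 | 200 | 160 | 1.20 | 1.25 |
| 300 | 240 | 200 | 1.25 | 1.20 |

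From 12 mg upward the gap is 1.2- to 2-fold in either case. Threefold occurs once in each: 3 vs 1 mg at the 3 mg level (case 1) and 3 vs 1 mg at the 6 mg level (case 2).

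**Time.** Section 5.2.3.2 gives 24 weeks as the minimum and 40 as the maximum for up-dosing, so the slack is 40 − 24 = 16 weeks. At the 2-week step each level of reduction costs 2 weeks. The tables differ by one level in cases 1 and 2, so each such reaction shifts the schedule by 2 of the 16 weeks.

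**Second epinephrine use, at home.** The second-use sentence gives 6 to 8 weeks at the reduced dose. The home sentence gives none, but Section 8.6.3.2 has a general default of 2 weeks. The difference is 6 − 2 = 4 to 8 − 2 = 6 weeks of the 16.

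**The case against.** The strongest reply is that Section 8.6.3.2 already answers case 1. It says that severity guides reductions, and that symptomatic treatment adds to dose reduction and does not replace it. Section 8.6.2 likewise treats medication as a supplement to dose adjustment. On that reading an antihistamine cannot cancel a Table 12 reduction. This has weight and favors Table 12 as a matter of text, but it is not a precedence rule and does not limit the Table 13 sentence. Nor does it settle case 2. If Table 12 simply governed, the site-epinephrine rule in Table 13 would have no effect for mild or moderate reactions, and Section 8.6.3.2 itself defers to Table 13 for re-escalation timing after epinephrine.

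Three further readings soften the conflict:
- The instruction to continue may mean only that the child stays in up-dosing, since the same cell uses similar words for a child on a reduced dose. That is possible. But the next sentence reserves a reduction for more than 2 doses, so the natural reading for 1 or 2 doses is no reduction.
- The sentence may be meant for tolerated mild symptoms, which Section 8.6.1.2 allows to be treated with up to 2 antihistamine doses. That is plausible but not stated.
- The previous tolerated dose might be 2 levels down. Table 12 glosses it that way only for chronic or recurrent mild symptoms, and this would not resolve case 1.

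Figure 3, which shows the Table 12 algorithm, was missing from the text available for review. It might address medication.

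**Conclusion.** The two tables conflict in cases 1 and 2, and the passages must be reconciled. With severity and treatment held fixed, the next doses differ 1.2- to 2-fold from 12 mg upward and threefold only at 3 mg (case 1) and 6 mg (case 2). This rests on reading the previous tolerated dose as 1 level down and on Figure 3 not supplying a rule. The two home-epinephrine points are lesser ambiguities: 1 vs 2 levels after a severe reaction, where 2 levels satisfies both tables and Table 13's silence does not cancel the monitor discussion; and a timing difference of about 4 to 6 weeks after a second use.

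Stronger readings are not supported:
- A reader might line up 120, 80 and 40 mg as a threefold range for one reaction at 120 mg. That compares an antihistamine-only child with one given epinephrine. For one treatment the clash is 120 vs 80 mg or 80 vs 40 mg.
- A reader might extend the conflict to severe reactions generally. Section 8.6.2 says these usually need epinephrine, and when it is given at the site both tables go down 2 levels.
- A reader might conclude that children will miss the 40-week limit because of this. One such reaction moves the schedule by 2 of 16 weeks, and nothing in the documents shows how often reactions would accumulate.

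No view is taken on which action is clinically right.

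**What to change.** Amend Section 8.6.3.2 so that:
1. it states which table governs when severity and medication point to different actions;
2. the antihistamine-only sentence in Table 13 names the reactions it covers;
3. the home-epinephrine sentence is aligned with the severe row of Table 12 and with the second-use sentence of Table 13, including the time at the reduced dose;
4. Figure 3 is checked against the result.

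The sponsor's clinical team decides the intended action in each case. The cost is table wording in a protocol amendment and a memo to sites, with no new procedures or subjects.
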